11.6.2.8 Dermatologic Events

Treatment-emergent rash has been associated with atezolizumab. The majority of cases of rash were mild in severity and self-limited, with or without pruritus. A dermatologist should evaluate persistent or severe rash or pruritus. A biopsy should be considered unless contraindicated. For specific management guidelines please see Table 10.

Table 10. Management Guidelines for Dermatologic Events

Adverse Event	Management
Dermatologic event, Grade 1	
Continue atezolizumab.Consider treatment with topical corticosteroids and/or other symptomatic therapy (e.g., antihistamines).
Dermatologic event, Grade 2	
Continue atezolizumab.Consider subject referral to dermatologist.Initiate treatment with topical corticosteroids.Consider treatment with higher-potency topical corticosteroids if event does not improve
Dermatologic event, Grade 3	
Withhold atezolizumab for up to 12 weeks after event onset.Refer subject to dermatologist.Initiate treatment with 10 mg/day oral prednisone or equivalent, increasing dose to 1-2 mg/kg/day if event does not improve within 48-72 hours.If event resolves to Grade 1 or better, resume atezolizumab.^bIf event does not resolve to Grade 1 or better while withholding atezolizumab, permanently discontinue atezolizumab and contact Sponsor.
Dermatologic event, Grade 4	
Permanently discontinue atezolizumab and contact the Sponsor.^c 
a. Atezolizumab may be withheld for a longer period of time (i.e., >12 weeks after event onset) to allow for corticosteroids (if initiated) to be reduced to ≤10 mg/day oral prednisone or equivalent. The acceptable length of the extended period of time must be agreed upon by the investigator and the Sponsor.
 
b. If corticosteroids have been initiated, they must be tapered over ≥1 month to ≤10 mg/day oral prednisone or equivalent before atezolizumab can be resumed.
 
c. Resumption of atezolizumab may be considered in subjects who are deriving benefit and have fully recovered from the immune-related event. Subjects can be rechallenged with atezolizumab only after approval has been documented by both the investigator (or an appropriate delegate) and the Sponsor

11.6.2.9 Neurologic Disorders

Myasthenia gravis, Guillain-Barré syndrome, and meningoencephalitis have been observed with single agent atezolizumab. Subjects may present with signs and symptoms of sensory or motor neuropathy. Diagnostic work-up is essential for an accurate characterization to differentiate between alternate etiologies. For specific management guidelines please see Table 11.

Table 11. Management Guidelines for Neurologic Disorders, Including Meningoencephalitis

Adverse Event	Management
Immune-related neuropathy, Grade 1	
Continue atezolizumab.Investigate etiology.
Immune-related neuropathy, Grade 2	
Withhold atezolizumab for up to 12 weeks after event onset.^aInvestigate etiology.Initiate treatment as per institutional guidelines.If event resolves to Grade 1 or better, resume atezolizumab.^bIf event does not resolve to Grade 1 or better while withholding atezolizumab, permanently discontinue atezolizumab and contact the sponsor
Immune-related neuropathy, Grade 3 or 4	
Permanently discontinue atezolizumab and contact the Sponsor.^cInitiate treatment as per institutional guidelines.

Adverse Event	Management
Myasthenia gravis and Guillain-Barré syndrome (any grade)	
▪ Permanently discontinue atezolizumab and contact the Sponsor.^c▪ Refer subject to neurologist.▪ Initiate treatment as per institutional guidelines.▪ Consider initiation of 1-2 mg/kg/day oral or IV prednisone or equivalent.
Immune-related meningoencephalitis, all grades	
▪ Permanently discontinue atezolizumab and contact the Sponsor.^c▪ Refer subject to neurologist.▪ Initiate treatment with 1-2 mg/kg/day IV methylprednisolone or equivalent and convert to 1-2 mg/kg/day oral prednisone or equivalent upon improvement.▪ If event does not improve within 48 hours after initiating corticosteroids, consider adding an immunosuppressive agent.▪ If event resolves to Grade 1 or better, taper corticosteroids over ≥ 1 month.

IV=intravenous

- a. Atezolizumab may be withheld for a longer period of time (ie, >12 weeks after event onset) to allow for corticosteroids (if initiated) to be reduced to ≤ 10 mg/day oral prednisone or equivalent. The acceptable length of the extended period of time must be agreed upon by the investigator and the Sponsor.
- b. If corticosteroids have been initiated, they must be tapered over ≥ 1 month to ≤ 10 mg/day oral prednisone or equivalent before atezolizumab can be resumed.
- c. Resumption of atezolizumab may be considered in subjects who are deriving benefit and have fully recovered from the immune-related event. Subjects can be rechallenged with atezolizumab only after approval has been documented by both the investigator (or an appropriate delegate) and the Sponsor

11.6.2.10 *Immune-Related Meningoencephalitis*

Immune-related meningoencephalitis is an identified risk associated with the administration of atezolizumab. Immune-related meningoencephalitis should be suspected in any subject presenting with signs or symptoms suggestive of meningitis or encephalitis, including, but not limited to, headache, neck pain, confusion, seizure, motor or sensory dysfunction, and altered or depressed level of consciousness. Encephalopathy from metabolic or electrolyte imbalances needs to be distinguished from potential meningoencephalitis resulting from infection (bacterial, viral, or fungal) or progression of malignancy, or secondary to a paraneoplastic process. All subjects being considered for meningoencephalitis should be evaluated urgently with a CT scan and/or MRI scan of the brain to evaluate for metastasis, inflammation, or edema. If deemed safe by the treating physician, a lumbar puncture should be performed and a neurologist should be consulted. For specific management guidelines.

11.6.2.11 *Immune-related Nephritis*

Immune-related nephritis is an identified risk associated with the administration of atezolizumab. Immune-related nephritis is a relatively rare complication of checkpoint inhibitor therapy with the most common reported underlying pathology being acute tubulo-interstitial nephritis (ATIN). The most common presentation is asymptomatic increase in creatinine levels. In the absence of alternative etiologies (e.g., prerenal and postrenal causes, and concomitant medications), immune-related nephritis is defined as renal dysfunction requiring steroids treatment and/or confirmed by biopsy. For specific management guidelines, please see Table 12.

Table 12. Management Guidelines for Immune-Related Nephritis

Adverse Event	Management
Immune-related nephritis, Grade 2	
Withhold atezolizumab and contact Sponsor.Refer subject to renal specialistInitiate treatment as per institutional guidelines and consider renal biopsy and supportive measures.Corticosteroids and/or additional immunosuppressive agents should be administered as clinically indicated.
Immune-related nephritis, Grade 3-4	
Permanently discontinue atezolizumab and contact Sponsor.Refer subject to renal specialistInitiate treatment as per institutional guidelines and consider renal biopsy and supportive measures.Corticosteroids and/or additional immunosuppressive agents should be administered as clinically indicated.

11.6.2.12 Systemic Immune Activation

Systemic immune activation is a rare condition characterized by an excessive immune response. Given the mechanism of action of atezolizumab, systemic immune activation is considered a potential risk when given in combination with other immunomodulating agents. Systemic immune activation should be included in the differential diagnosis for subjects who, in the absence of an alternate etiology, develop a sepsis-like syndrome after administration of atezolizumab, and the initial evaluation should include the following:

- Complete blood count (CBC) with peripheral smear
- Prothrombin time (PT), partial thromboplastin time (PTT), fibrinogen, and D-dimer
- Ferritin
- Triglycerides
- AST, ALT, total bilirubin
- Lactate dehydrogenase (LDH)
- Complete neurologic and abdominal examination (assess for hepatosplenomegaly)
- Serum sample for cytokine analysis

If systemic immune activation is still suspected after the initial evaluation, atezolizumab should be withheld with the provision of appropriate supportive medical care, including corticosteroid therapy. The Sponsor should be contacted for additional recommendations. Please see Table 13.

Table 13. Systemic Immune Activation

Systemic Immune Activation	
Major Criteria	Minor Criteria

Fever $\geq 38.5^{\circ}\text{C}$ (on more than one occasion)Ferritin $> 3000 \text{ ng/mL}$	
SplenomegalyHemophagocytosis

Systemic Immune Activation		
Major Criteria		Minor Criteria
		Number of Criteria

▪ Cytopenias
Grade 2 in two or more lineages▪ ≥ 2 age-adjusted SD elevation soluble IL-2 receptor▪ Severe multi-organ dysfunction▪ Decreased fibrinogen		BM, spleen or LN 
▪ Elevated GGT or LFTs (AST/ALT/tBili)▪ Elevated triglycerides▪ Elevated LDH▪ Decreased natural killer-cell activity
Consistent with systemic immune activation	4 criteria	Permanently discontinue atezolizumab and contact the Sponsor. Consider referring to an immunologist for evaluation Consider treatment with methylprednisolone, or equivalent, or the best way of treatment according to the physician's judgement.
Probable systemic immune Activation	3 major criteria OR 2 major criteria AND 3 minor criteria	Depending on clinical severity, subject can be treated as per "Consistent with systemic immune activation" or "Possible systemic immune activation" case definition. Contact the Sponsor for additional recommendations
Possible systemic immune Activation	1 major criteria	Consider methylprednisolone (1g IV QD) Contact the Sponsor for additional recommendations. As per "Consistent with systemic immune activation" recommendations if no improvement or clinically worsening

BM = bone marrow; GGT = gamma-glutamyl transpeptidase; IL-2 = interleukin-2; IV = intravenous; LFT = liver function test; LN = lymph node; QD = once daily; tBili = total bilirubin.
 
Notes: Criteria adapted from a Delphi Survey of 26 experts regarding helpful criteria in the positive diagnosis of Hemophagocytic Syndrome in adult subjects (Hejblum G. et al PLoS One, April 2014; Volume 9, Issue 4). Standard-of-care for systemic immune activation has not been established. Case reports and recommendations have been published for cytokine release syndrome (Lee 2014, Maude 2014, Teachey 2013), and based on etiologic similarities, these practices have been incorporated into the above treatment recommendations.
 
These recommendations do not replace clinical judgment and are intended as suggested guidance.
		

11.6.2.13 Infusion-related Reactions

No premedication is indicated for the administration of atezolizumab in Cycle 2. Subjects who experience an infusion-related reaction (IRR) with Cycle 2 of atezolizumab may receive premedication with antihistamines or antipyretics/analgesics (e.g., acetaminophen) for subsequent infusions. Metamizole (dipyrone) is prohibited in treating atezolizumab associated IRRs, due to its potential for causing agranulocytosis. Table 14 provides management guidelines for atezolizumab IRRs in Cycle 2.

Severity	Management
Grade 1	
• Reduce infusion rate to half the rate being given at the time of event onset.• After the event has resolved, the investigator should wait for 30 minutes while delivering the infusion at the reduced rate.

Severity	Management
	
• If tolerated, the infusion rate may then be increased to the original rate
Grade 2	
• Interrupt atezolizumab infusion.• Administer aggressive symptomatic treatment (e.g., oral or IV antihistamine, anti-pyretic, glucocorticoids, epinephrine, bronchodilators, oxygen).• Restart only after the symptoms have adequately resolved to baseline grade.• The infusion rate at restart should be half of the infusion rate that was in progress at the time of the onset of the IRR.• At next cycle, administer oral premedication with antihistamine and anti-pyretic and monitor closely for IRR.
Grade 3-4	
• Stop infusion.• Proper medical management which may include oral or IV antihistamine, anti-pyretic, glucocorticoids, epinephrine, bronchodilators, and oxygen• Discontinue atezolizumab.• Contact the Sponsor if atezolizumab is discontinued.

IRR = infusion-related reaction; IV = intravenous.

For subsequent cycles, infusion-related reactions should be managed according to institutional guidelines.

11.7 Disposition of Used Supplies

The blisters, cartons or bottles either used by the subjects or unused, must not be destroyed until the monitor has verified the accountability of the IMP.

During the trial, at the pre-defined visits, and at termination, patients must return all used and unused study drug supplies, and the return of these unused study drug supplies must be recorded. Returned supplies must not be re-dispensed.

All unused vials or capsules of study drug must be destroyed in an appropriate manner according to the standard practice at each study center. Destruction of such supplies will be documented, and a representative of the sponsor will verify disposition records.

No other utilization of the bosutinib and atezolizumab intended for use in this study is authorized by the Sponsor. The principal investigator or his/her designee will be responsible for the appropriate handling and disposition of residual study drugs. Each site is responsible for proper and careful destruction of study drug returned by patients.

11.8 Inventory of Unused Supplies

Periodically throughout the study and at its conclusion, a representative of the sponsor will conduct an inventory of unused study drugs. At the completion of the trial, a final study drug accountability review will be conducted. Any discrepancies must be investigated. All unused study drug must be destroyed on site following the standard operating procedures of the investigative site.

12 VISIT SCHEDULE AND ASSESSMENTS

12.1 Schedule of Events

Details on scheduling and sample collection are described in Tables 14-17. The tables 14 and 15 for 1st group of patients (first 10 patients included), and the tables 16 and 17 for 2nd group of patients (the last 26 patients included).

All data obtained from these assessments must be recorded in the source documentation. The CRF will not be used as a source document for any study data.

Please maintain a special awareness of the assessments of the primary and secondary endpoints.

All visits should be completed on the designated day or as close as possible. However, the windows allowed by protocol will be:

- For visits that take place every two weeks, the window will be ± 3 days.
- For visits that take place every 4 weeks, the window will be ± 3 days.
- For visits that take place every 3 cycles (every 12 weeks), and the End of Treatment visit, the window allowed will be ± 14 days.

For this purpose, a cycle equal to 28 days (4 weeks) will be defined and one month will be considered to be equivalent to one cycle.

Table 14. Schedule of Assessments 1st and 2nd Therapies for the First 10 Patients

The following visit schedule will apply if the atezolizumab dose does not need to be adjusted during 2nd therapy due to DLTs. If the dose of atezolizumab has to be modified to the 840 mg every two weeks, additional visits will be scheduled for the administration of atezolizumab. The only procedure to be conducted during these additional visits is the administration of atezolizumab

1 st Group of Patients (The 10 First Patients)		1 st Therapy		2 nd Therapy													
VISIT	Visit 0	Visit 1	Visit 2	Visit 3	Visit 4	Visit 5	Visit 6	Visit 7	Visit 8	Visit 9	Visit 10	Visit 11	Visit 12	Visit 13	Visit 14	Visit 15	Visit 16
Cycle	Screening / Baseline	Cycle 1		Cycle 2		Cycle 3		Cycle 4	Cycle 5	Cycle 6	Cycle 7	Cycle 8	Cycle 9	Cycle 10	Cycle 11	Cycle 12	Cycle 13
Day within Cycle (Visit Window ± 3 Days)	-28/-1	1	15	1	15	1	15	1	1	1	1	1	1	1	1	1	1
Consecutive Days in the Study (D)	-28/-1	D1	D15	D29	D43	D57	D71	D85	D113	D141	D169	D197	D225	D253	D281	D309	D337
Informed Consent	X																
Eligibility	X	X ⁽¹⁾															
Inclusion/Exclusion Criteria (Checklist)	X	X ⁽¹⁾															
Medical/Surgical History and Demographics	X																
Recent Medication Prior to First Dose of IMP	X	X ⁽¹⁾															
Leukemia Diagnosis and Prior Cancer Therapy	X																
Sokal Risk Score	X																
Vital Signs	X	X ⁽¹⁾	X ⁽¹⁾	X ⁽¹⁾	X ⁽¹⁾	X ⁽¹⁾	X ⁽¹⁾	X ⁽¹⁾	X ⁽¹⁾	X ⁽¹⁾	X ⁽¹⁾	X ⁽¹⁾	X ⁽¹⁾	X ⁽¹⁾	X ⁽¹⁾	X ⁽¹⁾	
Weight	X	X ⁽¹⁾		X ⁽¹⁾				X ⁽¹⁾									
Height	X																
12-Lead Electrocardiogram	X			X ⁽¹⁾	As clinically indicated												
Physical Examination and Extra-medullary Leukemia Involvement	X	X ⁽¹⁾	X ⁽¹⁾	X ⁽¹⁾				X ⁽¹⁾				X ⁽¹⁾		X ⁽¹⁾		X ⁽¹⁾	
ECOG	X	X ⁽¹⁾		X ⁽¹⁾				X ⁽¹⁾									
Blood Sample for BCR-ABL1 Assessment	X			X ⁽¹⁾				X ⁽¹⁾									

1 st Group of Patients (The 10 First Patients)		1 st Therapy		2 nd Therapy														
VISIT	Visit 0	Visit 1	Visit 2	Visit 3	Visit 4	Visit 5	Visit 6	Visit 7	Visit 8	Visit 9	Visit 10	Visit 11	Visit 12	Visit 13	Visit 14	Visit 15	Visit 16	
Cycle	Screening / Baseline	Cycle 1		Cycle 2		Cycle 3		Cycle 4	Cycle 5	Cycle 6	Cycle 7	Cycle 8	Cycle 9	Cycle 10	Cycle 11	Cycle 12	Cycle 13	
Day within Cycle (Visit Window ± 3 Days)	-28/-1	1	15	1	15	1	15	1	1	1	1	1	1	1	1	1	1	
Consecutive Days in the Study (D)	-28/-1	D1	D15	D29	D43	D57	D71	D85	D113	D141	D169	D197	D225	D253	D281	D309	D337	
Complete Blood Count with Differential	X	X ⁽¹⁾	X ⁽¹⁾	X ⁽¹⁾				X ⁽¹⁾			X ⁽¹⁾			X ⁽¹⁾			X ⁽¹⁾	
Chemistry	X ⁽²⁾	X ⁽¹⁾		X ⁽¹⁾⁽²⁾				X ⁽¹⁾⁽²⁾			X ⁽¹⁾⁽²⁾			X ⁽¹⁾⁽²⁾			X ⁽¹⁾⁽²⁾	
Serology	X																	
Bone Marrow Aspirate and Cytogenetic, if no-CCyR	X							X			X			X			X	
Pregnancy Test		X		X		X		X	X	X	X	X	X	X	X	X	X	
Immunological Studies	X			X ⁽¹⁾													X ⁽¹⁾	
Adverse Events	Medical History	Continuous																
Concomitant Medications	Medical History	Continuous																
Dispensing or Return of Bosutinib		X ⁽⁴⁾						X			X			X			X	
Atezolizumab Administration				X	X	X	X	X	X	X	X	X	X	X	X	X	X	

(1): The tests will be performed before IMP dose administration.

(2): Determination of lipase and amylase levels included.

(3): If the patient achieves CCyR, the cytogenetic assessment is not necessary.

(4) Dispense only bosutinib treatment.

Table 15. Schedule of Assessments 3rd Therapy for the first 10 patients

1 st Group of Patients	3 rd Therapy					
VISIT	Visit 17	Visit 18	Visit 19	Visit 20	Visit 21 (EOT)	Visit 22 (EOS)
Cycle	Cycle 14	Cycle 17	Cycle 20	Cycle 23	Cycle 25	Follow-up
Day within Cycle (Visit Window ± 14 Days)	1	1	1	1	29	28 days after the last dose
Consecutive Days in the Study (D)	D365	D449	D533	D617	D700	D728
Vital Signs	X ⁽¹⁾	X	X	X	X	X
Weight	X ⁽¹⁾	X	X	X	X	X
12-Lead Electrocardiogram	As clinically indicated					X
Physical Examination and Extra-Medullary Leukemia Involvement	X ⁽¹⁾	X	X	X	X	X
ECOG	X ⁽¹⁾	X	X	X	X	X
Blood Sample for BCR-ABL1 Assessment		X	X	X	X	
Complete Blood Count with Differential	X ⁽¹⁾	X	X	X	X	X
Chemistry	X ⁽¹⁾		X		X	X
Bone Marrow Aspirate and Cytogenetic, if No CCYR	X	X	X	X	X	X
(2)Pregnancy Test	X	X	X	X	X	X
Immunological Studies	X ⁽¹⁾				X	X
Adverse Events	Continuous					
Concomitant Medications	Continuous					
Dispensing or Return of Bosutinib	X	X	X	X	X (Return)	

(1): The tests will be performed before bosutinib administration

(2): Between visits to the center, the patient will perform a pregnancy test each month at her house.

Table 16: Schedule of Assessments 3rd Phase for Other 26 Patients

2 nd Group of patients (The Next 26 Patients)		1 st Therapy		2 nd Therapy												
VISIT	Visit 0	Visit 1	Visit 2	Visit 3	Visit 4	Visit 5	Visit 6	Visit 7	Visit 8	Visit 9	Visit 10	Visit 11	Visit 12	Visit 13	Visit 14	
Cycle	Screening / Baseline	Cycle 1		Cycle 2	Cycle 3	Cycle 4	Cycle 5	Cycle 6	Cycle 7	Cycle 8	Cycle 9	Cycle 10	Cycle 11	Cycle 12	Cycle 13	
Day within Cycle (Visit Window ± 3 Days)	-28/-1	1	15	1	1	1	1	1	1	1	1	1	1	1	1	
Consecutive Days in the Study (D)	-28/-1	D1	D15	D29	D57	D85	D113	D141	D169	D197	D225	D253	D281	D309	D337	
Informed Consent	X															
Eligibility	X	X ⁽¹⁾														
Inclusion/Exclusion Criteria (Checklist)	X	X ⁽¹⁾														
Medical/Surgical History and Demographics	X															
Recent Medication Prior to First Dose of IMP	X	X ⁽¹⁾														
Leukemia Diagnosis and Prior Cancer Therapy	X															
Sokal Risk Score	X															
Vital Signs	X	X ⁽¹⁾	X ⁽¹⁾	X ⁽¹⁾	X ⁽¹⁾	X ⁽¹⁾	X ⁽¹⁾	X ⁽¹⁾	X ⁽¹⁾	X ⁽¹⁾	X ⁽¹⁾	X ⁽¹⁾	X ⁽¹⁾	X ⁽¹⁾		
Weight	X	X ⁽¹⁾		X ⁽¹⁾		X ⁽¹⁾			X ⁽¹⁾			X ⁽¹⁾			X ⁽¹⁾	
Height	X	As clinically indicated														
12-Lead Electrocardiogram	X			X ⁽¹⁾	As clinically indicated											
Physical Examination and Extra-medullary Leukemia Involvement	X	X ⁽¹⁾	X ⁽¹⁾	X ⁽¹⁾		X ⁽¹⁾			X ⁽¹⁾			X ⁽¹⁾			X ⁽¹⁾	
ECOG	X	X ⁽¹⁾		X ⁽¹⁾		X ⁽¹⁾			X ⁽¹⁾			X ⁽¹⁾			X ⁽¹⁾	
Blood Sample for BCR-ABL1 Assessment	X			X ⁽¹⁾		X ⁽¹⁾			X ⁽¹⁾			X ⁽¹⁾			X ⁽¹⁾	
Complete Blood Count with Differential	X	X ⁽¹⁾	X	X ⁽¹⁾		X ⁽¹⁾			X ⁽¹⁾			X ⁽¹⁾			X ⁽¹⁾	
Chemistry	X ⁽²⁾	X ⁽¹⁾		X ⁽¹⁾⁽²⁾		X ⁽¹⁾⁽²⁾			X ⁽¹⁾⁽²⁾			X ⁽¹⁾⁽²⁾			X ⁽¹⁾⁽²⁾	

2 nd Group of patients (The Next 26 Patients)		1 st Therapy		2 nd Therapy												
VISIT	Visit 0	Visit 1	Visit 2	Visit 3	Visit 4	Visit 5	Visit 6	Visit 7	Visit 8	Visit 9	Visit 10	Visit 11	Visit 12	Visit 13	Visit 14	
Cycle	Screening / Baseline	Cycle 1		Cycle 2	Cycle 3	Cycle 4	Cycle 5	Cycle 6	Cycle 7	Cycle 8	Cycle 9	Cycle 10	Cycle 11	Cycle 12	Cycle 13	
Day within Cycle (Visit Window ± 3 Days)	-28/-1	1	15	1	1	1	1	1	1	1	1	1	1	1	1	
Consecutive Days in the Study (D)	-28/-1	D1	D15	D29	D57	D85	D113	D141	D169	D197	D225	D253	D281	D309	D337	
Serology	X															
Bone Marrow Aspirate and Cytogenetic, if no-CCyR	X					X				X			X			
Pregnancy Test		X		X	X	X	X	X	X	X	X	X	X	X	X	
Immunological Studies	X			X ⁽¹⁾											X ⁽¹⁾	
Adverse Events	Medical History	Continuous														
Concomitant Medications	Medical History	Continuous														
Dispensing or Return of Bosutinib		X ⁽⁴⁾				X			X			X			X	
Atezolizumab Administration				X	X	X	X	X	X	X	X	X	X	X	X	

(1): The tests will be performed before IMP dose administration.

(2): Determination of lipase and amylase levels included.

(3): If the patient achieves CCYR, the cytogenetic assessment is not necessary.

(4) Dispense only bousutinib treatment.

Table 17. Schedule of assessments 3rd Therapy for Other 26 patients

2 nd Group of Patients	3 rd Therapy					
VISIT	Visit 15	Visit 16	Visit 17	Visit 18	Visit 19 (EOT)	Visit 20 (EOS)
Cycle	Cycle 14	Cycle 17	Cycle 20	Cycle 23	Cycle 25	Follow-up
Day within Cycle (Visit Window ± 14 Days)	1	1	1	1	29	28 days after the last dose
Consecutive Days in the Study (D)	D365	D449	D533	D617	D700	D728
Vital Signs	X ⁽¹⁾	X	X	X	X	X
Weight	X ⁽¹⁾	X	X	X	X	X
12-Lead Electrocardiogram	As clinically indicated					X
Physical Examination and Extra-Medullary Leukemia Involvement	X ⁽¹⁾	X	X	X	X	X
ECOG	X ⁽¹⁾	X	X	X	X	X
Blood Sample for BCR-ABL1 Assessment		X	X	X	X	
Complete Blood Count with Differential	X ⁽¹⁾	X	X	X	X	X
Chemistry	X ⁽¹⁾		X		X	X
Bone Marrow Aspirate and Cytogenetic, if No CCYR	X	X	X	X	X	X
⁽²⁾ Pregnancy Test	X	X	X	X	X	X
Immunological Studies	X ⁽¹⁾				X	X
Adverse Events	Continuous					
Concomitant Medications	Continuous					
Dispensing or Return of Bosutinib	X	X	X	X	X (Return)	

(1): The tests will be performed before bosutinib administration.

(2): Between visits to center, the patient will perform a pregnancy test at her house.

The following describes the procedures/tests required for this study:

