12.19 Adverse Events and Concomitant Medications

AEs and concomitant medications will be recorded continuously throughout the study, starting on the date of the first administration of the study medication, and, at least, up to the 28-day follow-up visit after the last dose of treatment. New and updated AEs and concomitant medications will be reported within the treatment period; ongoing AEs thought to be at least possibly study-drug related; and all ongoing SAEs should be followed at least every 4 weeks until they resolve to baseline (or to NCI CTCAE, v5.0 grade ≤ 1), stabilize, or are considered to be chronic/irreversible (see section 13 Adverse Events reporting, for more information). Those relevant events that start before the first administration of the study drug will be recorded in the clinical history of the subject.

A maximum discontinuation of 1 month is allowed for the treatment with bosutinib if required due to the onset of adverse events, investigator decision, or other major circumstances. If a subject discontinued treatment for more than one month he/she will be withdrawn from the study and the appropriate follow-up procedures will be conducted. Regarding atezolizumab treatment, fail to administrate up to 3 out of the 11 administrations scheduled will be allowed for a patient to continue in the study. If, for some reasons, atezolizumab could not be administered 4 or more times, during the course of the study, the subject will be withdrawn from the study and the appropriate follow-up procedures will be conducted. All deviations from the scheduled treatments regime shall be recorded in the patients' clinical history and the eCRF and explained if required.

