12.21 End of Study. Follow-up Safety Procedures

All AEs ongoing or starting within 28 days after end of treatment must be recorded in the eCRF. After this time, ongoing AEs thought to be at least possibly study-drug related, as well as all ongoing SAEs, should be followed at least every 4 weeks until they resolve to baseline (or to NCI CTCAE, v5.0 grade ≤ 1), stabilize, or are considered to be chronic/irreversible.

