13.4 Reporting Period

The investigator shall report all SAEs and AESIs to FTH ([contact]) and Pfizer without undue delay but not later than 24 hours from the time he/she has knowledge of these events. The investigator, where applicable, shall send a follow-up report to the sponsor to allow the sponsor to assess whether the serious adverse event has impact on the benefit-risk balance of the clinical trial. The initial and follow-up reports shall identify the trial subjects only by a subject identification code assigned in the trial, specific for each of them.

For all screened patients, beginning at the time of the signature of the informed consent form and concluding 28 days after the last dose of the assigned study treatment or the investigator/patient decision to discontinue treatment or end of study (whichever occurs later), n-TEAEs, and AEs (both serious and non-serious) should be recorded on the eCRF.

Adverse event monitoring should start when the patient takes the study treatment for first time, and continued for at least 28 days following the last dose of study treatment or the investigator/patient decision to discontinue treatment (whichever occurs later).

AEs Ongoing after the Reporting Period: Any ongoing AE should be followed at least every 4 weeks, until they resolve to baseline, stabilize, or are considered to be chronic/irreversible.

SAEs starting after End of Study: SAEs occurring to a patient after the participation of that patient has ended should be reported to the sponsor if the investigator becomes aware of them. The investigator does not need to actively monitor subjects for AEs once the trial has ended.

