13.12 Required Follow-up for SAEs or AESIs

Routine follow-up should be conducted through and including 28 days after the last administration of assigned study treatment in the trial or the investigator/patient decision to discontinue treatment, whichever occurs later, in all patients, in order to monitor the occurrence of SAEs or AESIs. After this time, ongoing AEs thought to be at least possibly study-drug related, as well as all ongoing SAEs, should be followed at least every 4 weeks until they resolve to baseline (or to NCI CTCAE, v5.0 grade ≤ 1), stabilize, or are considered to be chronic/irreversible. The medical monitor may specify a longer follow-up period if required to assure the safety of the patient.

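### The printed ±14-day window lets the End of Study visit fall on day 14 after the last dose, two weeks before the required 28-day safety follow-up ends, with no later contact scheduled

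*Protocol*

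**What the plan says.** **Window in the tables.** Protocol Tables 15 (first 10 patients) and 17 (next 26) head the visit-day row with "Day within Cycle (Visit Window ± 14 Days". The row covers cycles 14, 17, 20 and 23, the EOT visit and the EOS visit. The EOS entry is "28 days after the last dose", shown as D728. No footnote exempts EOS from the window.

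**Window in the text.** Section 12.1 sets three rules: ±3 days for two-weekly visits, ±3 days for four-weekly visits, and ±14 days for 12-weekly visits and EOT. EOS is in none of them. The section also asks for visits on, or as near as possible to, the planned day.

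**Length of AE follow-up.**
- Section 12.21: "All AEs ongoing or starting within 28 days after end of treatment must be recorded in the eCRF".
- Section 13.4: monitoring is to be "continued for at least 28 days following the last dose of study treatment". Recording on the eCRF runs to 28 days after the last dose, the decision to discontinue "or end of study (whichever occurs later").
- Section 13.12, for serious AEs and AEs of special interest: "Routine follow-up should be conducted through and including 28 days after the last administration of assigned study treatment".
- Section 12.19, repeated in SAP 4.5: AEs are recorded "at least, up to the 28-day follow-up visit after the last dose of treatment".

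**After the visit.** EOS is the last column of both schedules. Section 13.4 asks for serious AEs arising after a patient's participation ends only if the investigator learns of them, and adds: "The investigator does not need to actively monitor subjects for AEs once the trial has ended".

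**The concern.** The protocol sets a 28-day minimum for post-treatment safety follow-up, but the only window printed for the visit that serves that follow-up opens at day 14. A site scheduling from the table could hold EOS two weeks early and have no further planned contact with the patient.

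Two things are at stake:

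- **AE ascertainment.** From the visit to day 28, new AEs would come to light only through an unscheduled call or because the patient reports them. Planned post-treatment observation could run from 14 to 42 days between patients, while SAP 6.5 summarises AEs as simple proportions.
- **Scheduled tests.** EOS carries the final blood count, chemistry and physical examination, and the only protocol-scheduled ECG after day 1 of cycle 2 (section 12.11). These could be done at day 14, and nothing in the AE rules asks for them to be repeated at day 28.

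Patients who stop during the combination are the most exposed, because section 6.3 gives atezolizumab a terminal half-life of 27 days.

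**Working it through.** **1. Reproduce the tabulated days.** With 28-day cycles, day 1 of cycle c is 1 + 28(c − 1). This gives D365, D449, D533 and D617 for cycles 14, 17, 20 and 23, all as tabulated. EOT is D700, and 700 + 28 = 728, which matches the EOS entry.

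**2. Apply the printed window to EOS.**
- Earliest: 728 − 14 = D714, which is 714 − 700 = 14 days after the last dose.
- Latest: 728 + 14 = D742, which is 42 days after the last dose.

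**3. Compare with the 28-day minimum.** At the earliest date, 28 − 14 = 14 days remain after the last scheduled contact, and 14/28 = 50%.

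**4. Try other readings of the EOS window.**

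| Reading | Earliest EOS (days after last dose) | Required days after the visit |
|---|---|---|
| Table header, ±14 | 14 | 14 of 28 (50%) |
| Treated as a four-weekly visit, ±3 | 25 | 3 of 28 (10.7%) |
| No window, as section 12.1 is silent | 28 | 0 of 28 |

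The result therefore depends on which reading a site adopts, and the documents do not settle it.

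**5. Check a one-day mismatch.** EOT is labelled day 29 of cycle 25. Cycle 25 starts on D673 (1 + 28 × 24), so day 28 is D700 and day 29 would be D701. Taking D701 as the last dose moves EOS to D729 and the window to D715–D743, which is still 14 to 42 days after the last dose.

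**6. Separate the visit from the recording duty.** Sections 12.21, 13.4 and 13.12 fix the 28 days by reference to the end of treatment, the last dose or the last administration, not to the visit. The share of AE recording that a site may drop is therefore 0 of 28 days. The 50% is the share of the period with no scheduled contact left. Only the sentence in section 12.19 and SAP 4.5 is tied to the visit. A day-14 visit would satisfy that sentence alone, but not the other three sections.

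**7. Identify who is affected.**
- *Completers:* the last scheduled atezolizumab infusion is D337. To EOT this is 700 − 337 = 363 days, or 363/27 ≈ 13.4 half-lives, so residual atezolizumab is not the issue for them.
- *Stopping during the combination:* on the terminal half-life alone, the fraction left 14 days after an infusion is 2^(−14/27) ≈ 0.70. Section 12.20 also allows the early-termination EOT visit up to 14 days after the last dose or the decision to stop. If the printed window applies, EOT and EOS could fall on the same day. That needs the latest EOT and the earliest EOS together.

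**The case against.** A reader might infer that the EOS visit closes AE collection, and so that a compliant site could lose half of the required follow-up. The documents do not support that. Section 12.19 and SAP 4.5 make the visit a floor, section 13.4 takes the latest of several end points, and a site that stopped recording at day 14 would breach sections 12.21, 13.4 and 13.12. The release from active monitoring in section 13.4 refers to the end of the trial, and does not clearly free a site from following a patient between days 14 and 28.

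A reader might also try to turn the gap into a share of AEs missed. That would need no capture at all after the visit, and assumptions about AE timing and the spread of visit dates. The documents give no basis for these.

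Further points on the other side stand:
- Section 12.1 does not grant EOS ±14 days, and several assessment sections (12.9 to 12.15) place it at 28 days. The day-14 visit comes from the table header, so this is a conflict between text and table rather than a clear permission.
- An early visit moves the tests; it does not remove them. Blood count and chemistry are also taken at EOT, and further ECGs are allowed when clinically indicated.
- AEs already ongoing are followed at least every four weeks in any case.
- AE summary tables cover the on-treatment period (protocol 15.3.2, SAP 6.9), and the documents do not say whether that includes the 28 days after treatment. An effect on the primary summaries is therefore not shown.

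None of this supplies a contact at day 28. The obligation to record is clear, but the scheduled means of meeting it can fall two weeks short.

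**Conclusion.** The point holds as a schedule inconsistency worth correcting. The header of Tables 15 and 17, read as printed, permits the last scheduled safety contact on day 14, against a 28-day minimum stated in three sections and a section 12.1 that gives EOS no window. At the extreme, 14 of 28 days follow the last planned contact. The gap is 3 days if a ±3-day rule is read in, and none if EOS is held on its nominal day.

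The conclusion assumes that sites schedule from the table header and that the same window is used for early stoppers, for whom no separate EOS schedule is given. The requirement to record AEs to day 28 is intact. What is weakened is how reliably AEs are ascertained in the last days and when the final tests are done. The practical consequence is greatest for patients who stop during the combination. The header applies to both groups, 10 + 26 = 36 planned patients.

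**What to change.** - In section 12.1, and as a note to the EOS column of Tables 15 and 17, give EOS its own window that does not open before day 28 after the last dose. With 0/+14 days as an example, a completer's EOS would fall on D728 to D742, and 0 of the 28 days would follow the visit.
- Alternatively, keep the option of an early visit but schedule a contact at day 28 to collect AEs. This covers AE capture but leaves the laboratory tests and ECG at the earlier date.
- State that the same rule applies to patients who stop early, so that their EOT and EOS visits cannot coincide.
- Keep ±14 days for the other third-therapy visits.

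The cost is one line of text and a column note in two tables, with slightly less freedom in scheduling the last visit. No treatment rule changes.
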